1.2.4. Modifications from the Statistical Section in the Final Protocol

There are no modifications compared to protocol amendment 6.

1.2.5. Revision History for SAP Amendments

This is the first version of SAP.

2. INVESTIGATION PLAN

2.1. Study Design and Randomization

This is a phase 3 randomized, double-blind, placebo-controlled study in adults/adolescent subjects (≥ 12 years) and pediatric subjects (< 12 years of age) who are household contacts of the first known household member infected with SARS-CoV-2 (index case). All subjects in the study are asymptomatic (having no active respiratory or non-respiratory symptoms consistent with COVID-19) at the time of screening. The index case will have a diagnosis of SARS-CoV-2 infection using a diagnostic test, e.g., RT-PCR, antigen test, or other test format (approved or with Emergency Use Authorization issued by the US FDA or by local health authority). Randomization will be performed by individual study subjects, not by households. Some of the index cases of household contacts in this study may be participating in a separate treatment study (R10933-10987-COV-2067).

[figure not shown]
Randomization will be performed by site and stratified for assigning subjects in a 1:1 allocation ratio to placebo or REGN10933+REGN10987 [1200 mg (600 mg of each mAb SC). Randomization stratifications are test results (positive, negative, or unavailable) of a local diagnostic assay for SARS-CoV-2 (e.g., molecular assay such as RT-PCR assay for SARS-CoV-2 or a SARS-CoV-2 antigen test) from appropriate samples, e.g., nasopharyngeal (NP), oropharyngeal (OP), nasal, or saliva, and age group (< 12 years, ≥ 12 to < 18 years, ≥ 18 to < 50 years, or ≥ 50 years). For pediatric subjects (< 12 years), the weight group (≥ 20 kg, ≥ 10 to < 20 kg, and < 10 kg) will be used as an additional stratification factor.

The study was originally planned to enroll 2000 adult and adolescent subjects. A blinded analysis of approximately 25% of enrolled subjects in this study was performed, demonstrating that higher than expected seropositivity was observed in cohort A. In addition, an unblinded administrative analyses was performed on the data based on 554 subjects to verify assumptions and adequacy of sample size. The subjects who were included in the administrative assessment will not be included in the final efficacy analysis. Thus, sample size was increased to accommodate higher seropositivity rate and the unblinded administrative assessment. The total study population was planned to be approximately 3500 adult and adolescent subjects (~3150 subjects in cohort A and ~350 subjects in cohort B) including 554 cohort A subjects in the administrative assessment and approximately 250 pediatric subjects < 12 years old (~225 subjects in cohort A1 and 25 subjects in cohort B1), with household contact exposure to individual with a confirmed SARS-CoV-2 infection.

Statistical analyses will be conducted separately in each cohort. For the purpose of the study analysis, cohorts A, A1, B, and B1 are independent. As specified earlier, the 554 subjects in the administrative assessment will not be included in the final efficacy analyses (first step analysis) however, these subjects will be included in the safety analyses. Also, the final efficacy analysis (first step analysis) will include only subjects randomized on or before January 28, 2021. The total number of subjects to be included in the first step analysis is approximately 2459. The subjects randomized after January 28, 2021 will remain blinded until the final analysis but will not be part of any formal statistical testing.

For each subject, the study comprises 3 periods: a 1-day screening/baseline period, a 1-month EAP, and a 7-month follow-up period (See [Figure 1](#)).

Figure 1: Study Flow Diagram

The schedule of events tables for this study can be found in the Appendix 10.2.

2.2. Sample Size and Power Considerations

2.2.1. Cohort A

The primary hypothesis is the reduction in the proportion of symptomatic RT-qPCR (broad-term) confirmed SARS-CoV-2 infections in seronegative subjects. To calculate the sample size to achieve at least 90% power for seronegative subjects in cohort A, it is assumed that the statistical hypothesis will be tested in a 2-sided test. Based on the administrative assessment results among 409 seronegative subjects in cohort A, an approximately 50% reduction of infection (symptomatic or asymptomatic) compared to placebo group and a 100% reduction of symptomatic infection compared to placebo group was observed. Due to the small sample size in the administrative assessment, it was assumed, for the purpose of assessing study power, that an approximately 50% reduction or greater in symptomatic infections compared to the placebo group will be expected for the final primary efficacy analysis.

In this household study design, the number of subjects per household, the correlation between subjects and symptomatic infection rates within a household are unknown. To detect a relative risk of 0.5 (i.e., 50% reduction of the assumed 10% attack rate in the placebo arm), equivalent to an odds ratio of 0.47, power was calculated compared to the p-value of 0.05 based on 2000

simulations in 1248 subjects from 430 households (i.e., assuming an average household size of 2.9 seronegative subjects). **Table 1** provides power calculations by varying degrees of correlation within household. In all cases, the power of the study is >90% using a generalized linear model with the generalized estimation equation (GEE) approach assuming a compound symmetry covariance matrix.

Table 1: Simulated Power for Household Design (1248 Subjects over 430 Households)

Placebo Attack Rate	REGN10933+ REGN10987 Attack Rate	Correlation within Household	Average Odds Ratio REGN10933+REGN10987 versus Placebo	Power
10%	5%	0.1	0.485	0.914
10%	5%	0.2	0.485	0.934
10%	5%	0.3	0.480	0.956
10%	5%	0.4	0.481	0.972
10%	5%	0.5	0.476	0.983
10%	5%	0.6	0.478	0.999

At least 1980 subjects will need to be enrolled in cohort A to have a minimum of 1248 seronegative subjects, assuming that 10% of subjects drop out, and 30% of subjects are seropositive at baseline.

The correlation among subjects within each household, the rates for seronegativity, and the rates for seropositivity will be monitored in a blinded fashion. The 2 assumptions, that 90% of randomized subjects will have a baseline negative RT-qPCR and be assigned to cohort A and that 70% of these subjects in cohort A are seronegative, will be monitored periodically to ensure that there will be a sufficient number of seronegative subjects (~1248) enrolled in Cohort A to be included in the primary analysis. This will maintain the planned statistical power.

2.2.2. Cohort B

The primary endpoint in asymptomatic seronegative subjects in cohort B is the proportions of subjects who subsequently develop signs and symptoms (broad term) within 14 days of a positive RT-qPCR test result at baseline or during the EAP.

The sample size of Cohort B is based on the frequency of finding positive subjects while enrolling Cohort A and assumes that approximately 10% of subjects in a household are already positive for SARS-CoV-2 by RT-qPCR at baseline. Among approximately 3500 adult and adolescent subjects that will be enrolled in cohort A or cohort B, the number of subjects expected in Cohort B is approximately 220 or higher, including 200 seronegative subjects. Assuming that 50% of infected placebo subjects at baseline will develop symptoms, 200 seronegative subjects in cohort B will provide >90% power to detect a relative risk of 0.5, using a 2-sided Fisher's exact test at an alpha level of 0.05.

3. ANALYSIS POPULATIONS

In accordance with guidance from the International Conference of Harmonization of Technical Requirements for Registration of Pharmaceuticals for Human Use (ICH) guideline ICH E9 Statistical Principles for Clinical Trials ([ICH, 1998](#)), the following population of analysis will be used for all statistical analysis.

3.1. The Efficacy Analysis Sets

Seronegative Modified Full Analysis Set (Seronegative mFAS-A) – Cohort A

The seronegative modified full analysis set for Cohort A (Seronegative mFAS-A) includes all randomized subjects aged 12 years and older who are laboratory confirmed negative for SARS-CoV-2 (per central lab PCR test) and who test negative for antibodies for SARS-CoV-2 (per central lab serology testing) at baseline.

Subjects included in the administrative assessment analysis are excluded from the Seronegative mFAS-A population.

Subjects will be analyzed based on the randomized treatment assignment. The seronegative mFAS-A population is the primary analysis population for the primary and secondary endpoints for Cohort A of this study unless specified otherwise.

Note: There are three antibody assays used for serology test: EuroImmun anti-S IgA, EuroImmun anti-S IgG, and Abbott anti-N IgG (Architect). Seronegative is defined as all available test results are negative. Seropositive is defined as 1 or more available test results are positive.

Seronegative Modified Full Analysis Set (Seronegative mFAS-A1) – Cohort A1

The seronegative modified full analysis set for Cohort A1 (seronegative mFAS-A1) includes all randomized subjects aged less than 12 years who are laboratory confirmed negative for SARS-CoV-2 (per central lab PCR test) and who test negative for antibodies for SARS-CoV-2 (per central lab serology testing) at baseline.

Subjects will be analyzed based on the randomized treatment assignment. The efficacy endpoints for Cohort A1 will be analyzed using the seronegative mFAS-A1 unless specified otherwise.

Seronegative Modified Full Analysis Set (Seronegative mFAS-B) – Cohort B

The seronegative modified full analysis set for Cohort B (seronegative mFAS-B) includes all randomized subjects aged 12 years and older who have laboratory confirmed positive tests at baseline for SARS-CoV-2 RT-qPCR and negative SARS-CoV-2 serology (both based on central lab testing) at baseline and are asymptomatic. Subjects will be analyzed based on the randomized treatment assignment. The primary and secondary efficacy endpoints for cohort B will be analyzed using the seronegative mFAS-B unless specified otherwise.

Seronegative Modified Full Analysis Set (Seronegative mFAS-B1) – Cohort B1

The seronegative modified full analysis set for Cohort B1 (seronegative mFAS-B1) includes all randomized subjects aged less than 12 years who have laboratory confirmed positive tests at baseline for SARS-CoV-2 RT-qPCR and negative SARS-CoV-2 serology (both based on central lab testing) at baseline and are asymptomatic. Subjects will be analyzed based on the randomized

treatment assignment. The efficacy endpoints for Cohort B1 will be analyzed using the seronegative mFAS-B1 unless specified otherwise.

3.2. The Safety Analysis Set (SAF)

The safety analysis set (SAF) includes all randomized subjects who received at least 1 dose or part of a dose of study drug. Subjects in the SAF will be analyzed based on the treatment received (as treated). In general, safety will be evaluated by study cohort: SAF-A (Cohort A), SAF-B (Cohort B), SAF-A1(Cohort A1), and SAF-B1 (Cohort B1). However, injection site reactions will also be based on all cohorts combined.

3.3. Pharmacokinetic Analysis Set

The PK analysis set includes all subjects who received any study drug and who had at least 1 non-missing drug concentration measurement following study drug administration. Subjects will be analyzed based on actual treatment received.

3.4. Immunogenicity Analysis Sets

3.4.1. Anti-drug Antibodies Analysis Set

The ADA analysis set (AAS) includes all subjects who received study drug and had at least 1 non-missing ADA result after study drug administration. Subjects will be analyzed based on the actual treatment received

3.4.2. Neutralizing Antibody Analysis Set

The NAb analysis set (NAS) includes all subjects who received any study drug and who are either negative in the ADA assay or positive for ADA with at least one non-missing result in the NAb assay after first dose of the study drug. Subjects who are ADA negative are set to negative in the NAb analysis set. Subjects will be analyzed according to the treatment actually received.

4. ANALYSIS VARIABLES

For each subject, demographic and baseline characteristics will be obtained from the last available value up to the date of the first study treatment administration (i.e., baseline definition). For subjects randomized but not treated, the baseline value is defined as the last available value prior to or on the date of randomization. If a subject was randomized over once, the latest randomization record will be used for analysis.

4.1. Demographic and Baseline Characteristics

The following demographic variables will be summarized:

- Age in years (continuous and categorical variable for subjects ≥ 12 years will be categorized as follows: ≥ 12 to < 18 , ≥ 18 to < 50 , ≥ 50 to < 65 , ≥ 65 to < 80 , ≥ 80 years)
- Sex (Male, Female)
- Race (American Indian or Alaskan Native, Asian, Black or African American, Native Hawaiian or Other Pacific Islander, White and Other, where “Other” may include, for example, not reported, unknown, and multiracial, etc.)
- Ethnicity (Hispanic or Latino with further subgroups [Black Hispanic or Latino and White Hispanic or Latino], not Hispanic or Latino with further subgroups [Black not Hispanic or Latino and White not Hispanic or Latino], not reported, and unknown)

Baseline characteristic variables include:

- Weight (kg) (quantitative and qualitative variable for pediatric subjects: < 10 , ≥ 10 to < 20 , and ≥ 20)
- Height (cm)
- Body mass index (BMI) (kg/m^2) (quantitative and qualitative variable for subjects ≥ 12 years: < 30 and ≥ 30)
- Randomization strata: local RT-qPCR status and age
- Region (US vs ex-US) and country
- Total household size including the house member(s) not participating this study
- Number of study subjects within household and cohort
- Index case interaction and household risk factors (e.g., share a bedroom, share a common room, no one wears a mask in home, etc.) per eCRF
- Status of index case participating R10933-10987-COV-2067
- Total household members, including index case, who participate the R10933-10987-COV-2067
- Infection risks (e.g. healthcare worker (Yes/ No), received influenza vaccine in last 14 days (Yes/No), first responder (Yes/No), Need to contact strangers on a regular basis (Yes/No), etc.) per exposure risk factors eCRFs

- Baseline overall serology status and observed combinations of three serology antibody assays
- Viral load (log10 copies/mL) at baseline for subject in cohort B
- Days between baseline central RT-qPCR test and study drug administration
- Baseline high risk subjects with at least one of the following criteria:
 - ≥ 65 years of age
 - BMI ≥ 35
 - Chronic kidney disease
 - Diabetes
 - Immunosuppressive disease
 - Are currently receiving immunosuppressive treatment

Are ≥ 55 years of age AND have cardiovascular disease OR hypertension OR chronic obstructive pulmonary disease

4.2. Medical History

Medical history will be coded to a Preferred Term (PT) and associated primary System Organ Class (SOC) according to the latest available version of Medical Dictionary for Regulatory Activities (MedDRA®).

4.3. Pre-Treatment / Concomitant Medication

Medications/Procedures will be recorded from the day of informed consent until the end-of-study (EOS) visit. Medications will be coded to the ATC level 2 (therapeutic main group) and ATC level 4 (chemical/therapeutic subgroup), according to the latest available version of WHO Drug Dictionary (WHODD, Drug Global version SEP2020 B3). Subjects will be counted once in all ATC categories linked to the medication.

Prior medications/procedures: medications taken, or procedures performed prior to administration of the first study drug.

Concomitant medications/procedures during treatment-emergent EAP: medications taken or procedures performed in the period from the day of the first dose of study drug to 28 days after the last dose of study drug or to the last visit if a subject discontinue from the study, whichever is earlier. This includes medications that were started before the initiation of study treatment and are ongoing during the treatment-emergent EAP.

Concomitant medications/procedures during the treatment-emergent follow-up period: medications taken, or procedures performed from the day after the end of treatment-emergent EAP to the final study visit or started during the treatment-emergent EAP and are ongoing after treatment-emergent EAP.

4.4. Prohibited Medications

The definition of prohibited medications is described in the section 8.9 of the protocol. They will be reviewed and identified by the study clinician and reported in protocol deviations.

4.5. Efficacy Variable

Unless otherwise specified, the baseline assessment is the last available measurement prior to the date of the study treatment administration. For subjects randomized but not treated, the baseline value is defined as the last available value prior to the date of randomization. Unless otherwise specified, all efficacy endpoints will be analyzed based on seronegative subjects in the corresponding cohort.

The definitions of broad-term, strict-term, and CDC definition symptoms are as follows:

Strict term:

- Fever ($\geq 38^{\circ}\text{C}$) PLUS ≥ 1 respiratory symptom (sore throat, cough, shortness of breath)

OR

- 2 respiratory symptoms (sore throat, cough, shortness of breath)

OR

- 1 respiratory symptom (sore throat, cough, shortness of breath) PLUS ≥ 2 non-respiratory symptoms (chills, nausea, vomiting, diarrhea, headache, conjunctivitis, myalgia, arthralgia, loss of taste or smell, fatigue or general malaise)

Broad term:

ANY of the following:

1. Fever $\geq 38^{\circ}\text{C}$
2. Feverish
3. Sore throat
4. Cough
5. Shortness of breath/difficulty breathing (*nasal flaring**)
6. Chills
7. Nausea
8. Vomiting
9. Diarrhea
10. Headache
11. Red or watery eyes (*conjunctivitis*)
12. Body aches such as muscle pain or joint pain (*myalgia, arthralgia*)
13. Loss of taste/smell
14. Fatigue (*fatigue or general malaise or lethargy**)
15. Loss of appetite or poor eating/feeding
16. Confusion
17. Dizziness
18. Pressure/tightness in chest
19. Chest pain

20. Stomachache (*Abdominal pain**)
21. Rash
22. Sneezing
23. Runny nose
24. Sputum/phlegm
25. Other

**Signs and symptoms observed in pediatric subjects (age<12 years)*

CDC definition

At least two of the following symptoms: fever (measured, i.e., fever $\geq 38^{\circ}\text{C}$, or subjective, i.e., feverish), chills, rigors, myalgia, headache, sore throat, nausea or vomiting, diarrhea, fatigue, congestion or runny nose

OR

Any one of the following symptoms: cough, shortness of breath, difficulty breathing, new olfactory disorder, new taste disorder

OR

Severe respiratory illness with at least one of the following, clinical or radiographic evidence of pneumonia, acute respiratory distress syndrome (ARDS)

Note: Fever information will be collected from the fever assessment eCRF, and signs and symptoms will be collected from COVID-19 symptoms eCRF.

The following general rules will be used for efficacy variables and all SARS-CoV-2 RT-qPCR test results are based on the central lab testing:

- For cohort determination, qualitative PCR results from swabs taken prior to or within 2 hours of study drug administration will be used if there are no available test results prior to study drug administration.
- Quantitative values of viral load will be determined based on NP swabs only. For baseline viral load, only RT-qPCR results from swabs taken prior to dosing will be used.
- A positive infection will be defined based on any available RT-qPCR result (either NP, nasal or saliva) which is reported as “detected”. A negative infection will be defined based on all available RT-qPCR results (either NP, nasal or saliva) which are reported as “not detected”.
- Symptomatic SARS-CoV-2 infection (broad-term) is defined as a positive central lab SARS-CoV-2 RT-qPCR result (either NP, nasal or saliva) associated with signs and symptoms with the onset date occurring within 14 days of a positive RT-qPCR during the EAP.
- For subjects in Cohort B, symptomatic SARS-CoV-2 infection (broad-term) is defined as having at least one signs and symptoms with the onset date occurring within 14 days of a positive RT-qPCR (either NP, nasal or saliva) at baseline or during the EAP.

- Viral loads less than the lower limit of quantification of the PCR assay but with positive qualitative results will be set to half of the lower limit of quantification of the PCR assay; values with nondetectable RNA will be set to 0 log₁₀ copies/mL. Viral load values above the upper limit of quantification will be re-tested using the reflex test and the corresponding quantitative value will be used in the analysis.

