#### 4. ENDPOINTS

Endpoints are specified for study cohorts (as defined in Section 6.1.6).

Symptomatic SARS-CoV-2 infection is determined by a positive central lab SARS-CoV-2 RT-qPCR result during the EAP with signs/symptoms occurring within  $\pm 14$  days of a positive RT-qPCR.

The “strict-term”, “broad-term” and CDC definitions for signs/symptoms of SARS-CoV-2 infection is presented in Section 9.2.2.2.

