### 5.2. Efficacy Variables

The efficacy variables include measurements or test results for individual subjects of the following:

- A positive SARS-CoV-2 infection (ie, a positive RT-qPCR) will be defined based on any available RT-qPCR result (either NP, nasal or saliva) which is reported as “detected”. A negative infection (ie, a negative RT-qPCR) will be defined based on all available RT-qPCR results (either NP, nasal or saliva) which are reported as “not detected”
- Viral load ( $\log_{10}$  copies/mL) from RT-qPCR test
- Asymptomatic SARS-CoV-2 infection: positive RT-qPCR result of NP swab sample without any of the strict-term or broad-term SARS-CoV-2 infection signs and symptoms (specified in Section [9.2.2.2](#)) within the EAP
- Symptomatic infection based on strict-term SARS-CoV-2 infection signs and symptoms (for secondary endpoint): Positive strict-term symptomatic infection defined as SARS-CoV-2 infection signs and symptoms (specified in Section [9.2.2.2](#)) and a positive RT-qPCR that occurs within the EAP
- Symptomatic infection based on broad-term SARS-CoV-2 infection signs and symptoms (for secondary endpoints): Positive broad-term symptomatic infection defined as SARS-CoV-2 infection signs and symptoms (specified in Section [9.2.2.2](#)) and a positive RT-qPCR that occurs within the EAP
- Symptomatic infection based on CDC definition SARS-CoV-2 infection signs and symptoms (for secondary endpoints): Positive broad-term symptomatic infection defined as SARS-CoV-2 infection signs and symptoms (specified in Section [9.2.2.2](#)) and a positive RT-qPCR that occurs within the EAP
- Medically attended visits to ED or UCC due to SARS-CoV-2 infection: number of visits that occur after a positive RT-PCR result within the EAP
- Hospitalization due to SARS-CoV-2 infection (hospitalization status and days in hospital) within the EAP

- Days absent from daily responsibilities (eg, days missed from work, school, childcare, or eldercare) due to SARS-CoV-2 infection within the EAP
- Occurrence of laboratory-confirmed SARS-CoV-2 infection during follow-up period collected from spontaneously reported AEs

Detailed descriptions for assessing COVID-19 signs and symptoms and their temporal relationship with lab confirmed SARS-CoV-2 infection is provided in Section [9.2.2.2](#).

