### 9.2.2.2. COVID-19 Symptomology (Strict Terms, Broad Terms, and CDC Definition)

During each scheduled or unscheduled visit/contact, the investigator or sub-PI investigator, or designee (ie, nurse practitioner in countries where allowed by local law) will query the subject and/or subject's parent or guardian about adverse events the subject is experiencing or has experienced since the last visit/contact (eg, within the prior week if it is a weekly scheduled visit) and ask about all of the signs and symptoms associated with these adverse events including the start date, end date and severity of each. The investigator should avoid querying the subject and/or subject's parent or guardian by running a check-list of signs and symptoms, but rather allow the subject and/or subject's parent or guardian to spontaneously report everything that they presented.

All signs and symptoms related to the AEs, along with the corresponding start date, end date and severity should be documented in the subject's medical records (source document). As signs and symptoms may appear and resolve on different days and may precede or occur after the collection of NP swab sample for the SARS-CoV-2 RT-qPCR test, it is important that this detailed information be captured in the source document.

Independent of the results (positive or negative) of the SARS-CoV-2 RT-qPCR tests performed on samples collected from study subjects during the weekly or unscheduled visits, all adverse events must be documented in the AE CRF. Signs and symptoms related to the adverse events reported in the AE CRF and confirmed to be temporally related to a positive SARS-CoV-2 RT-qPCR test collected from the subject's NP swab sample will be reported on a separate CRF (individual sign or symptom with start date and end date, and associated severity).

For the purpose of the study's primary and secondary objectives, the assessment of association of symptomatic disease with SARS-CoV-2 infection (ie, diagnosis of strict term COVID-19, broad term COVID-19, and CDC definition of COVID-19) will be based on the strict term, broad term, and CDC COVID-19 definitions described below ([Table 7](#)) and the temporal relationship of the signs and symptoms with lab confirmed SARS-CoV-2 infection (based on central lab RT-qPCR test result).

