### Temporal Relationship of Signs and Symptoms with Positive RT-qPCR for Diagnosis of COVID-19

The onset date of signs/symptoms will utilize a  $\pm 14$  days window from the date of the positive SARS-CoV-2 RT-qPCR, so long as the signs/symptom onset does not precede a negative SARS-CoV-2 RT-qPCR test. That is, the onset date of symptomatic SARS-CoV-2 infection is defined as the date of the first sign/symptom that is consistent with a diagnosis of COVID-19 as determined by the investigator. The onset date must be after the last negative SARS-CoV-2 RT-qPCR and no more than 14 days prior to the first positive SARS-CoV-2 RT-qPCR or must occur on or before 14 days after the last positive SARS-CoV-2 RT-qPCR.

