#### 11.4.3. Efficacy Analyses

##### 11.4.3.1. Primary Efficacy Analysis

###### Cohort A

The cohort A primary efficacy endpoint described in Section 4.1.1 will be analyzed in the seronegative mFAS-A population (Section 11.3.1). All post-baseline efficacy assessments obtained up to last scheduled visit (day 29) in EAP will be included for the primary analysis.

In order to account for the correlation among subjects within a household and control the associated type 1 error inflation, a generalized linear model will be used to estimate the odds ratio between the treatment groups by using the GEE approach. This model estimates a single within-household correlation coefficient. The model will include the fixed category effects of treatment group (placebo versus REGN10933+REGN10987), region (US versus ex-US), and age ( $\geq 12$  to  $< 50$ ,  $\geq 50$  years). The model will use a compound symmetry covariance matrix and estimate the odds ratio between the treatment groups and corresponding 95% CI and p-value.

If the GEE model fails to converge due to most households containing only a single study subject in seronegative mFAS-A or the percentage of households in cohort A with only a single study subject is 70% or more, then a logistic regression model will be used, with treatment, region, and age group as fixed effects. The threshold of 70% was based on simulations of within-household

correlation which show the type I error rate is inflated and the power is decreased when the proportion of single-subject households is high. Additional details will be provided in the SAP. If the logistic regression model does not converge, an exact logistic regression will be used. The estimates of odds ratio, the corresponding 95% CI and p-value will be provided from logistic regression (or exact logistic regression) for comparison of REGN10933+REGN10987 against placebo group.

In cohort A, a subject will be considered having a symptomatic RT-qPCR confirmed SARS-CoV-2 infection (broad-term) during the EAP if any of the post-baseline RT-qPCR results during EAP are positive with at least 1 symptom within 14 days of a positive RT-qPCR result.

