4.5.1. Cohort A Primary Efficacy Variable

The primary efficacy variable in Cohort A is:

- Proportion of subjects who have a symptomatic RT-qPCR confirmed SARS-CoV-2 infection (broad-term) during the EAP

A symptomatic RT-qPCR confirmed SARS-CoV-2 infection during the EAP will be any positive post-baseline RT-qPCR obtained during the EAP in which the subject experiences COVID-19 related signs or symptoms within 14 days of a positive test.

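### The cohort A primary event has two symptom-onset rules: protocol 9.2.2.2 rules out onset before a negative RT-qPCR, while protocol Sections 4 and 11.4.3.1 and the SAP use a 14-day window alone

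*SAP*

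**What the plan says.** **Window alone.**
- Protocol Section 4 asks for a positive central-laboratory "RT-qPCR result during the EAP with signs/symptoms occurring within" 14 days either side of a positive.
- Protocol 11.4.3.1 (cohort A) counts a subject if any post-baseline results in the efficacy assessment period (EAP) "are positive with at least 1 symptom within 14 days of a positive RT-qPCR result".
- SAP 4.5 uses "associated with signs and symptoms with the onset date occurring within 14 days of a positive RT-qPCR during the EAP". SAP 4.5.1 counts any positive "in which the subject experiences COVID-19 related signs or symptoms within 14 days of a positive test". SAP 5.7.1 and the estimand in SAP Appendix 10.1 follow the same pattern.

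**Window plus a last-negative condition.**
- Protocol 9.2.2.2 states its scope as the study's "primary and secondary objectives, the assessment of association of symptomatic disease with SARS-CoV-2 infection". It then allows 14 days either side of the positive only if onset does not precede a negative test, and continues: "The onset date must be after the last negative SARS-CoV-2 RT-qPCR and no more than 14 days prior to the first positive SARS-CoV-2 RT-qPCR". An alternative limb allows onset up to 14 days after the last positive.
- Protocol 5.2 sends the reader there: "Detailed descriptions for assessing COVID-19 signs and symptoms and their temporal relationship with lab confirmed SARS-CoV-2 infection is provided in Section" 9.2.2.2.

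The window-only passages do not repeat the last-negative condition or cite 9.2.2.2 for timing. Section 4 cites it only for the symptom definitions. I found no statement of which section takes precedence.

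**Duration.** SAP 4.5.2 counts symptomatic weeks from the date of the first symptom. This endpoint is second in the cohort A key secondary hierarchy.

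**The concern.** These passages give different answers to the question of who had a primary event. The trial's own schedule can produce the disputed sequence. Swabs are weekly throughout the EAP (protocol 9.1.1, footnote 17), so a 14-day look-back can reach past an earlier negative. Protocol 6.1.4 also calls for an extra swab when infection is suspected, which creates negatives dated after onset.

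A programmer working from the SAP and a clinician working from 9.2.2.2 can therefore reach different event counts, and different durations, from the same records. If the choice is left until after unblinding, it could be made with knowledge of its effect.

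A smaller mismatch concerns which symptoms qualify. The synopsis and the broad-term text in 9.2.2.2 limit the broad term to 23 symptoms or fever, and protocol 3.2.5 says any one of 23 symptoms. The broad-term column of Table 7 ends with 'Other', and SAP 4.5 lists it as item 25, which is enough on its own.

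**Working it through.** The plan gives no figure to reproduce here, so the check sets the two rules side by side.

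**1. Onset days treated differently.** Inputs: nominal swabs on days 1, 8, 15, 22 and 29 (protocol Table 3); a subject negative until the first positive on day P; last negative on day N; onset day d of 2 or later, because active symptoms are excluded at entry (protocol 7.2.2).
- Window alone: 2 ≤ d ≤ P and P − d ≤ 14.
- With 9.2.2.2: also d > N.

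| P | N | Window alone | With 9.2.2.2 | Treated differently |
|---|---|---|---|---|
| 8 | 1 | days 2–8 (7) | days 2–8 (7) | 0 |
| 15 | 8 | days 2–15 (14) | days 9–15 (7) | 7 (days 2–8) |
| 22 | 15 | days 8–22 (15) | days 16–22 (7) | 8 (days 8–15) |
| 29 | 22 | days 15–29 (15) | days 23–29 (7) | 8 (days 15–22) |

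Onset on the day of the negative swab is treated as failing, because the operative sentence requires onset after it. If same-day onset were allowed, the counts would be 0, 6, 7 and 7.

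Unscheduled swabs can create a conflict even at P = 8. With onset on day 3, a symptom-triggered negative on day 4 and a positive on day 8, the window counts the onset and 9.2.2.2 does not.

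**2. What reclassifies a subject.** All three must hold: the subject becomes positive, a recorded symptom starts before an intervening negative, and no qualifying symptom starts after that negative. Day counts are therefore not event counts.

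**3. Timing of first positives.** Protocol 3.2.6 gives the only data, from the administrative assessment. Day-8 positivity was 10.3% of 223 placebo subjects (0.103 × 223 = 23) and 5.4% of 186 active subjects (0.054 × 186 = 10). The same section counts 21 and 9 infected subjects. The figures do not reconcile exactly, and these subjects are excluded from the seronegative mFAS-A. They still suggest that most first positives came at day 8, where the rules agree on the nominal schedule.

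**4. Weight of one reclassified event.** This shows leverage and is not an estimate of the effect. Arms of 1248/2 = 624.
- Design rates: 624 × 0.10 ≈ 62 and 624 × 0.05 ≈ 31, risk ratio 31/62 = 0.50. One extra active event gives 32/62 = 0.516; one extra placebo event gives 31/63 = 0.492.
- Placebo rate 8/223 = 3.6% (protocol 3.2.5) with an assumed risk ratio of 0.50: 624 × 0.036 ≈ 22 and 624 × 0.018 ≈ 11. One extra active event gives 12/22 = 0.545; one extra placebo event gives 11/23 = 0.478.

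**5. Duration.** Headache from day 3, negative on day 8, positive on day 15, cough on days 15–20, all symptoms over by day 20. SAP 4.5.2 gives (20 − 3 + 1)/7 = 2.6 weeks. Starting at the first onset that satisfies 9.2.2.2 gives (20 − 15 + 1)/7 = 0.9 weeks. This subject is a primary event under both rules; only the duration changes.

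**The case against.** **The SAP departs from the protocol without saying so.** A reader might infer this from SAP 1.2.4: "There are no modifications compared to protocol amendment 6". The documents do not support it. That section concerns the protocol's statistical section, and SAP 5.7.1 follows protocol 11.4.3.1 closely. The SAP is faithful to Section 11, and the disagreement lies between protocol sections.

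**The SAP governs programming and states one rule.** It does. But the protocol assigns the temporal relationship to 9.2.2.2 for the primary objective, so following the SAP alone leaves a protocol condition unapplied.

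**Sites filter these cases.** Under 9.2.2.2, only symptoms confirmed as temporally related to a positive go on the separate symptom form, and sites see the RT-qPCR results (protocol 3.2.3). This probably removes many unrelated early symptoms. It is not a derivation rule, however, and the form instructions are not in the documents. Fever comes from its own form (SAP 4.5), for which no entry rule is given.

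**9.2.2.2 is itself unclear.** This stands. Taken alone, the limb on 14 days after the last positive would admit a day-3 onset with a day-15 positive. Taken literally, the proviso on not preceding a negative would exclude anyone who later clears the virus. Reading the negative as the last one before the first positive makes the two sentences consistent, but the text should say so.

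**The opposite choice would also resolve the conflict.** True. A false-negative swab after true onset would make the last-negative rule drop a genuine event.

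**Conclusion.** The cohort A primary event is defined in two incompatible ways, and this should be settled before unblinding. It is a contradiction between stated rules and not a gap in detail.

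The number of subjects affected cannot be derived. It is probably small, given site confirmation and the apparent concentration of first positives at day 8. That judgement rests on administrative data that do not reconcile exactly and on the nominal swab schedule.

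Two stronger readings are tempting and not supported:
- A reader might infer from the table that about half of the later events are misclassified. It counts calendar days, and reclassification needs all three conditions in step 2 of the working.
- A reader might infer a bias in a known direction. Early symptoms unrelated to treatment would dilute the effect under the window-only rule, while false-negative swabs would cost genuine events under the other. The documents do not say which dominates.

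The 'Other' mismatch is real but separate, and its size is also unknown.

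**What to change.** Before the first-step database lock and unblinding, state one onset rule for the primary event and symptomatic duration. Section 9.2.2.2 is the detailed rule that 5.2 points to, so the natural course is to add this to SAP 4.5, 4.5.1, 4.5.2, 5.7.1 and Appendix 10.1 and to protocol Sections 4 and 11.4.3.1:

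> For onset before the first positive, onset must be after the last negative RT-qPCR preceding that positive, using actual swab dates and not the SAP 6.4 windowed results.

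The last clause is needed because SAP 6.4 keeps the worst result in an analysis window, so an unscheduled negative sharing a window with a positive would disappear. Reword 9.2.2.2 to the same reading, and make clear that the limb on 14 days after the last positive does not override it.

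Report by arm the events that meet only the 14-day window, and give the window-only result as a sensitivity analysis. Reconcile the 23-symptom wording with Table 7 and SAP item 25, and report by arm the events that qualify on 'Other' alone.

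Cost: wording in both documents, one derivation condition on dates already collected, one sensitivity analysis and two counts by arm. The downside is possibly a few fewer primary events.
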